10.6.17 Immediate tolerance after IP intake

Possible immediate reactions like rash, nausea, upper abdominal pain, dizziness, sensitivity to light, irritability, headache, heartburn and fatigue after the IP intake will be closely monitored if will appear; such reactions will be closely monitored and observed changes should be measured and recorded as AEs.

10.7 Premature Termination of the Study

The subject may withdraw from the study any time without giving reasons and without any disadvantageous consequences for his subsequent medical care. Furthermore, the subject should be withdrawn from the study if the investigator has the impression that it would be to the subject's detriment to continue the study.

In case of premature termination from the study the investigator should perform the following:

- physical examination
- vital signs (blood pressure, heart rate temperature and respiratory rate)
- body measurements (weight)

	Study Title	Bioavailability Study of COQUN ORAL FORMULATION (CoQ10) administered in Healthy Adults (CoQ10-01)		
	Study ID	VF-BAQ10/2018	Sponsor:	VISUFARMA SpA
	Date	March 03, 2018	Vers.	Final

- 12 lead ECG
- blood laboratory analysis (Hematology,) to be performed at investigator discretion whenever indicated by the subject health status
- record of concomitant medication
- adverse events

Note: If the subject did not receive any IP (i.e., premature termination between the ICF signature and the single dose phase) no further examination are necessary to be performed and subject will be declared screening failure.

10.8 Discussion of Study Design

This is an interventional, single-center, single- and multi-dose bioavailability study of COQUN ORAL FORMULATION in Healthy Adults with 2 treatments periods: a 100mg single dose phase of 1 day, and a multi dose 1 month period, with a 1 week washout between the two phases. Study population: 24 healthy adult volunteers.

The results demonstrated by numerous recent scientific studies regarding the antioxidative properties of CoQ10 provided a promising therapeutic potential for ameliorating oxidative stress-mediated mitochondrial dysfunction in ischemic retinal injury, as well as on preventing RGC apoptosis and loss in glaucoma-related models.

Considering that many factors can affect the Q10 blood level of people who are not taking a Q10 supplement: age, diet, disease, medications (for example, statin medications), it is expected that supplementing regularly with Q10 will raise the Q10 blood level, but much depends on the way in which the Q10 product has been prepared and much depends on the dosage. It was demonstrated that taking 30 milligrams or 50 milligrams of Q10 daily will not raise the Q10 level as much as taking 100 mg of Q10 daily will do, while taking 100 milligrams of Q10 twice daily will yield even greater gains in Q10 blood levels.

From the literature it is known that a well-absorbed Q10 supplement should over time raise the blood level to about 2.5 micrograms per milliliter if the individual is taking a 100-milligram dosage once a day, while if taken the same Q10 supplement in a dosage of 100 milligrams twice a day, its blood level should, over time, raise the steady-state Q10 blood level to somewhere in the area of 3.5 micrograms per milliliter. But, the attainable levels will vary from individual to individual, beside depending on the product itself as formulation.

COQUN ORAL FORMULATION, a food supplement based on Coenzyme Q10 MINIACTIVES®, innovative technology based on the modified release of active at certain time intervals (which is not affected by physiological variables such as pH, gastro-intestinal motility, presence of food and others) thanks to the presence of a permeable and insoluble multi-membrane polymer system, so thanks to its modified and controlled release technology, was conceived

	Study Title	Bioavailability Study of COQUN ORAL FORMULATION (CoQ10) administered in Healthy Adults (CoQ10-01)		
	Study ID	VF-BAQ10/2018	Sponsor:	VISUFARMA SpA
	Date	March 03, 2018	Vers.	Final

in order to allow the Coenzyme Q10 transport, without undergoing alterations and favoring its maximum absorption.

The dosing schedule in this study was planned to evaluate the best dosage for COQUN ORAL FORMULATION in order to reach a level of plasma concentration which might assure its antioxidant effect if taken on a regular basis.

Further studies are planned in case the results of this bioavailability study show positive results, in order to support the intended use for COQUN ORAL FORMULATION to be food support added to hypotonic pharmacological therapy in glaucoma patients, where the high oxidative stress linked to the pathology is well known.

11 ADVERSE EVENTS

11.1 Definition

11.1.1 Adverse Events

An AE is any untoward medical occurrence in a subject or clinical study subject administered a pharmaceutical product and which does not necessarily have to have a causal relationship with this treatment. An AE can therefore be any unfavorable and unintended sign (see list below), symptom, or disease temporarily associated with the use of a medicinal product, whether or not considered related to the medicinal product.

AEs can be:

- Drug reactions,
- Accidents,
- Illnesses with onset during the study,
- Exacerbation's (increase in severity or frequency of existing symptoms or appearance of a new symptom) of pre-existing illnesses,
- New illness or change in existing illness requiring new drug therapy or an increase in the dosage of an existing drug therapy,
- Any clinically significant changes from baseline detected concerning the physical examination, vital signs, ECG, or laboratory values.

The definition covers the entire study period, independent of whether IP was administered or not.

The most frequent symptoms and signs observed after CoQ10 intake might be mild insomnia, elevated levels of liver enzymes, rash, nausea, upper abdominal pain, dizziness, sensitivity to light, irritability, headache, heartburn, and fatigue

The investigator is responsible for ensuring appropriate clinical management of all (S)AEs until they are resolved or stabilize at a level acceptable to the investigator and the sponsor.

Note: any newly occurring disease or condition and/or a deterioration of a current disease or condition must be documented as adverse events in the source document and then transferred in the section AE of the CRF.

	Study Title	Bioavailability Study of COQUN ORAL FORMULATION (CoQ10) administered in Healthy Adults (CoQ10-01)		
	Study ID	VF-BAQ10/2018	Sponsor:	VISUFARMA SpA
	Date	March 03, 2018	Vers.	Final

The following applies to changes in laboratory values:

Laboratory alert limits are defined by an upper and a lower limit of the individual parameter. All values beyond these limits are considered possibly clinically significant. The investigator has to ensure that each parameter out of the normal range is checked for clinical significance. For any deviation beyond the alert limits detected at any visit after screening visit, the investigator has to document the change as an AE in the source document and CRF. No AE has to be recorded if the parameter already deviated from the alert limit at screening visit.

The following cases define conditions where values beyond alert limits should not be reported as an AE:

- Abnormal parameters that are obviously biological implausible (e.g. values, which are incompatible with life).
- Abnormal laboratory parameters caused by mechanical or physical influences on the blood sample (e.g. hemolysis) and marked as such by the laboratory on the laboratory report,

It is at the discretion of the investigator to document any change or trend over time in laboratory tests or vital signs as an AE if he considers the change to be clinically significant, even if the absolute value is within the alert limits or reference range. In case of clinically significant changes in laboratory values it is preferable to document the condition or disease suspected for the aberration.

Surgery and other invasive procedures that are planned prior to the start of the study do not have to be documented as AE. Planned procedures have to be recorded by the investigator in the source data at screening visit. In this context, it should be noted that surgery is usually not an AE but rather a measure to treat an AE. Therefore, a precise description of the medical event should be given.

The subject has to be instructed to inform the investigator immediately about all AEs and complete the subject diary in the periods during the study visits. During the treatment period visits, the AEs have to be documented in the CRF together with their intensity (mild, moderate or severe, refer to Section 11.1.3).

Any AE, which is in accordance with the above definition, has to be documented by the investigator, regardless of any consideration on causality.

11.1.2 Serious Adverse Events

Any untoward medical occurrence or response to a medicinal product that at any dose:

- Results in death,
- Is life threatening,
- Results in in-subject hospitalization or prolongation of existing hospitalization,
- Results in a persistent or significant disability/incapacity,
- Is a congenital anomaly/birth defect or,

	Study Title	Bioavailability Study of COQUN ORAL FORMULATION (CoQ10) administered in Healthy Adults (CoQ10-01)		
	Study ID	VF-BAQ10/2018	Sponsor:	VISUFARMA SpA
	Date	March 03, 2018	Vers.	Final

- Important AEs that are not immediately life-threatening or do not result in death or hospitalization but may jeopardize the subject or may require intervention to prevent one of the other outcomes listed.

A life-threatening AE is any adverse drug experience that places the subject at immediate risk of death from the reaction as it occurred, i.e., it does not include a reaction that, had it occurred in a more severe form, might have caused death.

Hospitalization is defined as any in-subject treatment covering more than one calendar day. Hospitalization does not include the following:

- Emergency Room/Accident and Emergency/Casualty Department visits,
- Out-patient/same-day/ambulatory procedures,
- Observation/short-stay units,
- Rehabilitation facilities,
- Hospice facilities,
- Respite care (e.g. caregiver relief),
- Skilled nursing facilities,
- Nursing homes,
- Custodial care facilities,
- Clinical research/Phase I units,
- Hospitalization in the absence of a precipitating, treatment emergent, clinical AE may meet criteria for "seriousness" but may not be considered a SAE:
 - Admission for treatment of a preexisting condition not associated with the development of a new adverse event or with a worsening of the pre-existing condition (e.g., for work up of persistent pre-treatment lab abnormality),
 - Social admission (e.g., subject has no place to sleep),
 - Administrative admission (e.g., for annual physical examination),
 - Protocol specified admission during a clinical study (e.g., for a procedure required by the study protocol),
 - Optional admission not associated with a precipitating clinical adverse event (e.g., for elective cosmetic surgery).

Prolongation of an existing hospitalization is defined as any extension of an in-patient hospitalization beyond the stay anticipated/required in relation to the original reason for the initial admission, as determined by the investigator or treating physician.

Prolongation in the absence of a precipitating, treatment emergent, clinical adverse event (i.e. not associated with the development of a new adverse event or worsening of a pre-existing condition) may meet criteria for "seriousness" but is not an adverse experience and thus is not subject to immediate reporting to the sponsor. Pre-planned treatments or surgical procedures will be recorded on the appropriate page of the CRF as soon as the investigator is informed.

	Study Title	Bioavailability Study of COQUN ORAL FORMULATION (CoQ10) administered in Healthy Adults (CoQ10-01)		
	Study ID	VF-BAQ10/2018	Sponsor:	VISUFARMA SpA
	Date	March 03, 2018	Vers.	Final

Disability is a substantial disruption of a person's ability to conduct normal life.

11.1.3 Intensity

In the course of the study, the investigator will determine whether any adverse events have occurred and will grade their intensity as follows:

Mild: Symptoms do not alter subject's normal functioning.

Moderate: Symptoms produce some degree of impairment to function, but are not hazardous, uncomfortable or embarrassing to the subject.

Severe: Symptoms hazardous to well-being, significant impairment of function or incapacitation.

11.1.4 Causal Relationship to Investigational Product

The investigator can assign the cause of an AE to the intake of the IP, or to another reason. The decision must be explained for each event. The investigator's final judgment on the causal relationship between the IP and the AE is based on the following scale:

Related: Reports of a reasonable temporal relation between the AE and the intake of the IP. There is no other explanation for the AE and subsidence or disappearance of the AE on withdrawal of the IP (dechallenge) and recurrence of the symptoms on restart at previous dose.

Probable: Reports including good reasons and sufficient information to assume a causal relationship in the sense that it is plausible, conceivable, or likely.

Possible: Reports containing sufficient information to indicate the possibility of a causal relationship in the sense of it not being impossible and not unlikely, although the connection may be uncertain or doubtful (e.g. due to missing data, insufficient evidence).

Not related: Reports of a clinical event, including laboratory test abnormality, with a temporal relationship to IP administration which makes a causal relationship improbable, and in which other drugs, chemicals, or underlying disease provide plausible explanations i.e., no reasonable suspected causal relationship to IP administration.

Not assessable: Reports suggesting an AE that cannot be judged because information is insufficient or contradictory, and that cannot be supplemented or verified.

11.1.5 Management and Follow-up of Adverse Events

The investigator is responsible for ensuring appropriate clinical management of all (S)AEs until they are resolved or stabilize at a level acceptable to the investigator and the sponsor. Appropriate clinical management of (S)AEs is at the discretion of the investigator.

11.1.6 Documentation and Reporting

11.1.6.1 Adverse Events

	Study Title	Bioavailability Study of COQUN ORAL FORMULATION (CoQ10) administered in Healthy Adults (CoQ10-01)		
	Study ID	VF-BAQ10/2018	Sponsor:	VISUFARMA SpA
	Date	March 03, 2018	Vers.	Final

All AEs have to be reported over the entire study period, i.e. the period from first (written Informed Consent) to last protocol-specific procedure.

All observed or reported AEs regardless of treatment group or suspected causal relationship to the IP will be recorded on the AE page(s) of the CRF. The investigator must assess all AEs for seriousness, severity, and relationship to the IP.

The investigator will follow all AEs, regardless of seriousness or severity, until the event or its sequel resolve or stabilize at a level acceptable to the investigator and the sponsor.

11.1.6.2 Serious Adverse Events

Reporting to CRO/sponsor

Any SAE or death must be reported immediately independent of the circumstances or suspected cause if it occurs or comes to the attention of the investigator at any time during the study within 30 days after the last administration of the IP. Completion of the study must be promptly reported if a causal relationship to IP is suspected.

The investigator is responsible for ensuring that any SAE, regardless of relationship to IP, is reported within 24 hours from its knowledge. SAEs must be documented on the SAE report forms provided by sponsor, in addition to the AE pages of the CRF.

The minimum information required from the investigator when reporting an SAE is as follows:

- Investigator's identification (name and center number),
- Protocol identification number,
- Subject identification number (randomization number),
- SAE description including criteria for seriousness and the immediate outcome.

All SAEs reports must be faxed directly to:

VISUfarma SpA

NAME: [name]

Role: Qualified Person for Pharmacovigilance

[contact]

[contact]

e-Mail: [contact]

A follow-up report must be done as soon as new information is available. Every SAE will be followed up until the outcome of the event is categorized as fatal, resolved completely, or resolved with sequel.

In the case of a subject's death, a summary of available autopsy findings must be submitted as soon as possible to the sponsor.

Reporting to Independent Ethics Committee/health authorities

The investigator is obliged to report AEs to the Ethics Committee and authorities according to local legal requirements.

	Study Title	Bioavailability Study of COQUN ORAL FORMULATION (CoQ10) administered in Healthy Adults (CoQ10-01)		
	Study ID	VF-BAQ10/2018	Sponsor:	VISUFARMA SpA
	Date	March 03, 2018	Vers.	Final

In accordance with applicable regulatory requirements, the investigator is obliged to notify the IEC/IRB as well as to the regulatory authorities of any suspected unexpected serious adverse reactions, including those notified to him by the sponsor, within expedited reported timelines. The investigator must obtain written acknowledgement of receipt of the SUSAR report from the Ethics Committee/regulatory authorities and forward a copy of this acknowledgement to the sponsor.

12 BIOSTATISTICAL METHODS

12.1 General

Due to the explorative aim of the study, descriptive statistics and confidence intervals at 90% level will be provided.

In particular, continuous variables will be presented as arithmetic mean values \pm standard deviation (SD) and median values with interquartile range; geometric means will be provided as well; for categorical variables absolute and percentage frequencies will be provided.

All data collected during the study visits and up to V5 (EOS) will be presented for the two groups.

Any major deviations from this plan, the reasons for such deviations, and all alternative or additional statistical analyses that may be performed will be explained in the Statistical Analysis Plan (SAP), which will give a detailed technical description of all statistical analyses. All deviations and/or alterations will be summarized in the Clinical Study Report (CTR).

12.2 Objective

To evaluate the best dosage for COQUN ORAL FORMULATION in order to reach a level of plasma concentration which might assure its antioxidant effect if taken on a regular basis.

12.3 Determination of Sample Size

The sample size for this study is not based on any power calculation.

24 subjects (12 for each arm) have been considered sufficient to obtain reliable results for the exploratory purposes of the study.

12.4 Analysis Sets

The following analysis sets will be considered in this study.

12.4.1 Safety Set

This set consists of all randomized subjects who sign informed consent and take at least one dose of study product.

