7 STUDY OBJECTIVES AND VARIABLES

7.1 OBJECTIVES

Primary objective:

The primary objective of this study is to evaluate the best dosage between 100mg OD or 100mg BID for COQUN ORAL FORMULATION in order to reach a level of plasma concentration which might assure its antioxidant effect if taken on a regular basis.

Secondary Objectives:

Secondary objectives of this study are:

- To evaluate the safety and tolerability COQUN ORAL FORMULATION following single dose of 100mg
- To evaluate the safety and tolerability of COQUN ORAL FORMULATION during the 1 month daily dose

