9.6 Methods of Assigning Subjects to Treatment Groups

Subjects who are eligible for the study will first be thoroughly informed about the aims and details of the study and in case the subject accepts to participate, the signed Informed Consent will be obtained, and the patient will receive the lowest screening number available.

If all required criteria for admitting a subject to the study are fulfilled, the investigator will proceed with the study procedures of the Screening visit (V1) and with the single dose administration of IP.

After the screening visit, subjects will have one week of wash-out period, then will be requested to return to the site for V2, during which Subjects will be randomly assigned to one of the two groups:

- group A: 12 adult healthy subjects will be given OD 100mg of COQUN ORAL FORMULATION, to be taken after dinner
- group B: the other 12 adult healthy subjects will be given BID a dose of 100 mg of COQUN ORAL FORMULATION, to be taken after lunch and after dinner

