10.6.10 IP administration

IP will be administered at site by the subject on Day -7 by intake of 1 IP capsule of 100mg, under investigator's supervision.

Subjects should be fasted for at least 10 h prior to and 2 h after administration. Water will not be permitted 1 hour before dosing dose and 1 hour post dosing.

Per protocol IP dose is 100mg.

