3. ANALYSIS SETS AND SUBGROUPS

3.1 Analysis sets

The following analysis sets will be considered in this study.

Safety Set

This set consists of all randomized subjects who sign informed consent and take at least one dose of study product.

Intention-to-treat Population

This set contains all randomized subjects.

Per Protocol Population

The per protocol population consists of all subjects who meet all inclusion/exclusion criteria and who do not have any major protocol deviation.

The primary endpoint will be evaluated on ITT and PP populations. Results obtained on the PP population will be considered as supportive of those obtained on the ITT set.

Secondary endpoints and safety assessment will be evaluated on the Safety set.

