5. STATISTICAL ANALYSIS: DEFINITIONS, DERIVATIONS, CALCULATIONS AND METHODOLOGY

5.1 Baseline Characteristics

5.1.1 Disposition of Subjects

Collected Variables:

- Treatment group assigned (categories: treatment 1/treatment 2) [CRF – Visit 2]
- Has the subject completed the study (yes, no) [CRF - EOS]
- Primary reason for the premature termination (free text) [CRF - EOS]
- Date of informed consent [CRF – Visit 1]
- Is the subject eligible for entering the study (yes, no) [CRF – Visit 1]
- Inclusion/exclusion criteria (yes, no) [CRF – Visit 1]
- Was the investigational product taken correctly? (yes, no) [CRF – Visit 3, 4, 5]

Derived Variables:

- whether the subject belongs to the :
 - safety set (subjects must have signed the informed consent and they must have taken at least one dose i.e. the answer to the question "Was the investigational product taken correctly" must be "yes" at least once)
 - ITT set (subjects must have been randomized)
 - PP set (subjects must have been randomized and they do not have major deviations)

Imputations for missing values:

If the date of last intake of study medication is not available, due to premature termination or other reasons, date of last investigational product intake (collected in the end of study form of the CRF) will be imputed.

Analysis Sets to be used for:	Tables	Table1: All subjects
	Listings	Tables 2,3, 4: ITT analysis set Listing 1: All subjects Listings 2, 3, 4: ITT analysis set
	Figures	Figure 1: All subjects Figure 2: ITT analysis set

Subject disposition will be summarized by treatment group as follows:

Table 1. Number of Subjects and Subjects Disposition (Total set)	Total number of subjects screened, randomized and number of subjects in analysis sets will be presented by treatment group. The percentage of subjects will be calculated relative to the number of all randomized subjects.
---	---

Table 2. Reasons for premature study termination (All Randomized Subjects)	For study termination and for premature discontinuation reason, a default frequency tabulation will be provided. The percentage of subjects will be calculated relative to the number of subjects who were randomized.
---	---

Table 3. Analysis Sets (All Randomized Subjects)	Subject analyses set status will be summarized for each treatment group, together with the reason(s) for exclusion from the Safety, ITT and PP
---	--

	Form	Form No.	1M-DMST-011-01-A1
	Statistical Analysis Plan	Page	Page 14 of 69
		Effective Date	07/05/2018

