- Related AEs: in the analysis related AEs will be defined as AEs for which the relationship with study device is assessed as "definitive" or "probable" or "possible"
- Severe AEs: in the analysis severe AEs will be defined as AEs for which the severity is assessed as "severe" or "life threatening"
- Subjects who prematurely terminated the Study Due to AE: in the analysis subjects who prematurely terminated the study due to AE are defined as those subjects with an adverse event for which the reason for early termination in the CRF end of study has been recorded as "adverse event"
- Death: death is defined as a fatal outcome of an AE.

Adverse events (AEs) will be reported on a per-subject basis. This implies that even if a subject reported the same event repeatedly, the event will be counted only once. In the latter case, the event will be assigned the worst severity and strongest relationship to the investigational study medication. The presentation of AEs is therefore restricted to the incidence per subject of AEs assigned to the Treatment Period.

Analysis Sets to be used for:	Tables	Safety analysis set
	Listings	Safety analysis set
	Figures	Not applicable

Adverse events will be summarized by default summary statistics by treatment group. Percentages will be calculated relative to the total number of subjects considered valid for the Safety analysis set.

Table 18. Summary of Adverse Events in the Single Dose Phase (Safety set)

Overview of AEs in the single dose phase including the:

- number of subjects with at least one AE.
- number of subjects with at least one device-related AE.
- number of subjects with at least one serious AE.
- number of subjects with at least one severe AE.
- number of subjects who prematurely terminated the study.
- Number of AEs
- Number of serious AEs
- Number of related AEs
- Number of severe AEs
- Number of deaths

Table 19. Summary of Adverse Events in the Multidose Phase (Safety set)

Overview of AEs in the multidose phase including the:

- number of subjects with at least one AE.
- number of subjects with at least one device-related AE.
- number of subjects with at least one serious AE.
- number of subjects with at least one severe AE.
- number of subjects who prematurely terminated the study.
- Number of AEs
- Number of serious AEs
- Number of related AEs
- Number of severe AEs
- Number of deaths

	Form	Form No.	1M-DMST-011-01-A1
	Statistical Analysis Plan	Page	Page 26 of 69
		Effective Date	07/05/2018

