8.2.1.3 Safety Analysis

Table 18. Summary of Adverse Events in the Single Dose Phase (Safety set)

Characteristic	Statistic	Treatment A (N=XXX)	Treatment B (N=XXX)	Total (N=XXX)
Number of Subjects With at Least One AE	n (%)	XXX (X.X%)	XXX (X.X%)	XXX (X.X%)
Number of Subjects With at Least One related AE	n (%)	XXX (X.X%)	XXX (X.X%)	XXX (X.X%)
Number of Subjects With at Least One serious AE	n (%)	XXX (X.X%)	XXX (X.X%)	XXX (X.X%)
Number of Subjects With at Least One severe AE	n (%)	XXX (X.X%)	XXX (X.X%)	XXX (X.X%)
Number of Subjects who Prematurely Terminated the Study Due to AE	n (%)	XXX (X.X%)	XXX (X.X%)	XXX (X.X%)
Number of AEs	n (%)	XXX (X.X%)	XXX (X.X%)	XXX (X.X%)
Number of serious AEs	n (%)	XXX (X.X%)	XXX (X.X%)	XXX (X.X%)
Number of related AEs	n (%)	XXX (X.X%)	XXX (X.X%)	XXX (X.X%)
Number of severe AEs	n (%)	XXX (X.X%)	XXX (X.X%)	XXX (X.X%)
Number of deaths	n (%)	XXX (X.X%)	XXX (X.X%)	XXX (X.X%)

N: Number of subjects in specified treatment group

n: Number of subjects with data available

%: Percentage based on N

Notes: a) serious AE are AE with seriousness recorded as "yes";
 b) related AE are AE with relationship with study device recorded as "definitive", "probable", "possible";
 c) severe AE are AE with severity recorded as "severe", "life threatening or disabling";
 d) Subjects who prematurely terminated the Study Due to AE are defined as those subjects with an adverse event for which the reason for early termination in the CRF end of study has been recorded as "adverse event".

 1MED Regulatory & Clinical Development	Form	Form No.	1M-DMST-011-01-A1
	Statistical Analysis Plan	Page	Page 48 of 69
		Effective Date	07/05/2018

Table 19. Summary of Adverse Events in the Multidose Phase (Safety set)

Characteristic	Statistic	Treatment A (N=XXX)	Treatment B (N=XXX)	Total (N=XXX)
Number of Subjects With at Least One AE	n (%)	XXX (X.X%)	XXX (X.X%)	XXX (X.X%)
Number of Subjects With at Least One related AE	n (%)	XXX (X.X%)	XXX (X.X%)	XXX (X.X%)
Number of Subjects With at Least One serious AE	n (%)	XXX (X.X%)	XXX (X.X%)	XXX (X.X%)
Number of Subjects With at Least One severe AE	n (%)	XXX (X.X%)	XXX (X.X%)	XXX (X.X%)
Number of Subjects who Prematurely Terminated the Study Due to AE	n (%)	XXX (X.X%)	XXX (X.X%)	XXX (X.X%)
Number of AEs	n (%)	XXX (X.X%)	XXX (X.X%)	XXX (X.X%)
Number of serious AEs	n (%)	XXX (X.X%)	XXX (X.X%)	XXX (X.X%)
Number of related AEs	n (%)	XXX (X.X%)	XXX (X.X%)	XXX (X.X%)
Number of severe AEs	n (%)	XXX (X.X%)	XXX (X.X%)	XXX (X.X%)

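### The Safety Set counts only randomised subjects, but everyone is dosed a week before randomisation, so a subject who stops in between appears in no adverse event output

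*Protocol*

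**What the plan says.** Protocol 12.4.1 gives the Safety Set as follows: "This set consists of all randomized subjects who sign informed consent and take at least one dose of study product". SAP 3.1 uses the same words and adds: "Secondary endpoints and safety assessment will be evaluated on the Safety set".

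Dosing comes before randomisation. Protocol 10.6.10 states: "IP will be administered at site by the subject on Day -7 by intake of 1 IP capsule of 100mg". Protocol 9.6 has subjects go through a one-week wash-out, and they "then will be requested to return to the site for V2, during which Subjects will be randomly assigned to one of the two groups". SAP 2.3 agrees.

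The first secondary objective in Protocol 7.1 reads: "To evaluate the safety and tolerability COQUN ORAL FORMULATION following single dose of 100mg". The set grid in SAP 5.2.2.1 assigns the Safety Set to all AE tables and listings, and the text fixes the denominator: "Percentages will be calculated relative to the total number of subjects considered valid for the Safety analysis set".

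SAP 5.1.1 then derives membership differently: "subjects must have signed the informed consent and they must have taken at least one dose i.e. the answer to the question" on correct intake has to be yes at least once. SAP 5.1.4 shows that this item is collected only at V3, V4 and V5. A separate Visit 1 item records whether the Day -7 dose was taken, but the derivation does not use it. SAP 6 declares no change from the protocol.

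**The concern.** A safety population should contain everyone exposed. Here exposure starts on Day -7 and eligibility for the set starts on Day 0, so subjects who leave in that week are excluded by definition. They include anyone who left because of an adverse event, which is the outcome the single-dose tables are meant to capture. The protocol foresees such exits: 8.4.1 and 8.4.3 cover withdrawal for an adverse event or by the investigator, and 10.5.1 releases subjects from V1 only if there has been no SAE.

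Tables 18 and 20 and the single-dose parts of Tables 22 and 23 are the only tabulated AE results for the first secondary objective. As planned, they describe only subjects who came back for V2. Single-dose vital signs (Table 24 at Visit 1, and Listing 23) carry the same restriction.

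The SAP 5.1.1 rule extends the problem to the multidose phase. Taking the product correctly is not the same as taking it. A randomised subject who stops early because of an adverse event and has no yes answer leaves the set. Because one set serves both phases, that subject also leaves the single-dose tables, despite a supervised dose on Day -7.

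**Working it through.** There is no planned figure to reproduce: Protocol 12.3 says the 24 subjects (12 per arm) do not come from a power calculation, and no drop-out rate is given.

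**Tracing a subject dosed on Day -7 who stops before V2**

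1. Not randomised, so outside the Safety Set under Protocol 12.4.1 and SAP 3.1.
2. Outside it under SAP 5.1.1 too. That rule does not repeat the word randomised, but the subject has no V3 or V4 answer and received no multidose product for a V5 answer to describe.
3. Therefore absent from Tables 18 to 23 and Listings 18 to 21.
4. Absent from Table 3 and Listing 4, which give reasons for exclusion from the sets but cover randomised subjects only.
5. Listing 1, as described in SAP 5.1.1, would show the termination but has no AE fields. Its shell is headed as covering screening failures only, a status that Protocol 10.7 reserves for subjects who received no product, so the subject could be missing there as well.

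**Single-dose phase: the Table 18 row "Number of Subjects who Prematurely Terminated the Study Due to AE"**

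Let x be the number stopping for an adverse event between Day -7 and V2 (assumed), with no returning subject later stopping for a single-dose event. Without replacement the planned table shows 0/(24 − x), and all dosed subjects give x/24. Protocol 8.4 allows conditional replacement; if it happens, the table shows 0/24 and all dosed subjects give x/(24 + x).

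| x | Shown, no replacement | All dosed | Shown, with replacement | All dosed |
|---|---|---|---|---|
| 1 | 0/23 | 1/24 = 4.2% | 0/24 | 1/25 = 4.0% |
| 2 | 0/22 | 2/24 = 8.3% | 0/24 | 2/26 = 7.7% |
| 3 | 0/21 | 3/24 = 12.5% | 0/24 | 3/27 = 11.1% |

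**Single-dose phase: subjects with any adverse event**

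Let a be the number of returning subjects with an event (assumed). Without replacement, shown = a/(24 − x) and all dosed = (a + x)/24. For a = 2:

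- x = 1: 2/23 = 8.7% against 3/24 = 12.5%
- x = 2: 2/22 = 9.1% against 4/24 = 16.7%
- x = 3: 2/21 = 9.5% against 5/24 = 20.8%

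For a = 0, 2 and 4 the shortfall is 4.2, 3.8 and 3.4 percentage points when x = 1, and 12.5, 11.3 and 10.1 points when x = 3.

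**Chance that at least one subject is lost**

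With an assumed probability q that a subject stops before V2 for any reason, the chance is 1 − (1 − q)^24: 38% for q = 2%, 71% for q = 5% and 92% for q = 10%.

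**Multidose phase: the same row in Table 19, one arm of 12**

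Let y be the number who stop for an adverse event and have no yes answer (assumed), with nobody else in the arm stopping for one. Shown = 0/(12 − y), and all exposed = y/12: 0/11 against 1/12 = 8.3%, and 0/10 against 2/12 = 16.7%.

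**The case against.** The strongest reply is that the effect may be zero. The study is exploratory, the exposure is one capsule in healthy volunteers, and the gap is seven days. Adverse events are still recorded and SAEs still reported under Protocol 11.1.6. This stands as to size, and the counts above are illustrations. It does not defend the definition, which has to be right before anyone knows who drops out.

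Second, the plan does not say to which phase wash-out events belong. The synopsis describes a one-day single-dose phase and a separate wash-out, while the SAP has AE tables for two phases only. The missing rule is a real gap and belongs in the fix. With only two phases, and with Protocol 12.9.1 promising AE summaries over V1 to V5, the single-dose tables are the natural place.

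Third, the loss is not wholly invisible. Listing 1 has columns for a termination reason and a comment, and Table 1 and Figure 1 show how many subjects were screened or consented and how many were randomised. That is fair, but these give a reason or a head count, not AE data.

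Fourth, the SAP 5.1.1 fault needs two things to happen: early stopping and no yes answer. Protocol 8.4 asks for a final visit, and a subject who took capsules as instructed until the event could be answered yes there. The exclusion therefore applies when that answer is no or the visit is missed. How often this would happen cannot be judged from the documents.

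**Conclusion.** The concern holds and should be fixed. As written, a subject dosed on Day -7 who does not reach V2 cannot appear in any AE table or AE listing, and SAP 5.1.1 contradicts both SAP 3.1 and the protocol on what counts as a dose. This follows from the text and needs no assumption.

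The size does need assumptions. One to three AE-related stops before V2 would be reported as none, in place of 4.2% to 12.5% of those dosed. One or two stops without a yes answer in a multidose arm would be reported as none, in place of 8.3% or 16.7%. If all 24 return and each has at least one yes, nothing is lost. Data collection and expedited reporting are unaffected; the fault lies in the planned outputs.

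**What to change.** - In Protocol 12.4.1, SAP 3.1 and SAP 5.1.1, define the Safety Set identically as all consented subjects who took at least one dose, including the Day -7 dose. Record the change in SAP 6.
- Derive membership from the Visit 1 intake item and from diary or accountability records of actual intake (Protocol 9.7), not from the item on correct intake.
- Use all subjects dosed at V1 for the single-dose outputs: Tables 18 and 20, the single-dose parts of Tables 22 to 24, and Listing 23. Include them in the AE listings. Show unrandomised subjects under Total or in a column of their own.
- Use subjects with at least one multidose capsule for Tables 19 and 21, the multidose parts of Tables 22 to 24, and Listing 22.
- State in one line the phase to which wash-out events are assigned.
- Update the set grids in SAP 5.2.2.1 and 5.2.2.2, extend Table 3 and Listing 4 to all dosed subjects, and align the Listing 1 shell heading with its text.

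Three further items are optional. The other Safety Set tables (5 to 7 and 9 to 12) could be treated in the same way. The first-intake date in SAP 4.4 should be reconciled with Protocol 12.9.1, because SAP 5.1.8 uses first intake to classify medication. If single-dose pharmacokinetics is also to use everyone dosed at V1, Protocol 12.7 and SAP 5.2.3 must both be amended.

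The cost is modest: text edits in two documents and revised shells for the safety tables and listings. No new data are needed. Visit 1 intake is already a CRF item, and diaries and capsule counts are already kept, although the compliance items in the SAP are yes/no only, so actual multidose intake would have to be brought in from those records.
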